****CONFIDENTIAL & PROPRIETARY****

List of Abbreviations and Definition of Terms

AE	Adverse Events
BPH	Benign Prostatic Hyperplasia
BRB	Biomedical Research Building
CNS	Central Nervous System
CRF	Case Report Form
CTCAE	Common Terminology Criteria for Adverse Events
eCRF	Electronic Case Report Form
ED	Erectile Dysfunction
EDITS	Erectile Dysfunction Inventory of Treatment Satisfaction
EDV	End Diastolic Velocity
GCP	Good Clinical Practice
HIPAA	Health Information Portability and Accountability Act
ICF	Informed Consent Form
ICH	International Conference of Harmonization
ICI	Intracavernosal Injection
IEC	Institutional Ethics Committee
IIEF	International Index of Erectile Function
IIEF-EF	Erectile Function Subdomain Score
IRB	Institutional Review Board
ISCI	Interdisciplinary Stem Cell Institute
MCID	Minimal Clinically Important Difference
mL	Milliliter
ng/dL	Nanograms Per Deciliter
PDE5i	Phosphodiesterase 5 inhibitor
PPP	Platelet Poor Plasma
PRFM	Platelet Rich Fibrin Matrix
PRP	Platelet Rich Plasma
PSV	Peak Systolic Velocity
RCT	Randomized Controlled Trial
SAE	Serious Adverse Events
SEP3	Sexual Encounter Profile
SOP	Standard Operating Procedure
SWT	Low-intensity Shockwave Therapy
TE-SAE	Treatment Emergent Serious Adverse Events
UM	University of Miami
VAS	Visual Analogue Pain Scale

Protocol Synopsis						
TITLE	COMBINING SHOCKWAVE THERAPY AND PLATELET RICH PLASMA FOR TREATING ERECTILE DYSFUNCTION IN DIABETIC MEN (COCKTAIL-DM)					
SPONSOR	Jniversity of Miami, Miller School of Medicine - Department of Urology					
PHASE OF STUDY	Phase I/II					
STUDY THERAPY	Autologous Platelet-Rich Plasma (PRP) + Low-intensity Shockwave Therapy (SWT)					
STUDY DESIGN	Single arm, Open Label, Pilot Trial					
ROUTE OF ADMINISTRATION	Intracavernosal Injection (PRP) + extracorporeal shockwave therapy (SWT)					
SUBJECT POPULATION	15 male subjects between the age of 30-80 with Mild or Mild-to-Moderate ED and controlled Diabetes Mellitus (DM)					
STUDY	Primary: To investigate biochemical markers of neo-angiogenesis in patients before and after PRP injection + SWT					
OBJECTIVES	Secondary: To study efficacy and incidence of adverse events and safety of PRP injection + SWT treatment in men with mild-moderate ED, as measured by IIEF.					
	15 men with Erectile Dysfunction (ED) of organic origin and Diabetes (Type 1 or Type 2), that meet all of the inclusion and none of the exclusion criteria, will be enrolled and will receive PRP+SWT.					

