3.1 Primary Endpoints

- Changes in markers of vasodilation (eNOS, nNOS), neo-angiogenesis (VEGF, CD-31), and systemic markers of endothelial function (EPCs, SDF-1α, and SCF).

3.2 Secondary Endpoints (efficacy):

- Differences in Doppler ultrasound parameters (PSV and EDV) from baseline to 6 months post-therapy.
- Treatment satisfaction as assessed by EDITS questionnaire in all subjects.
- Incidence of Serious Adverse Events experienced up to 6 months post-therapy.

3.3 Exploratory Endpoints:

- Change in IIEF-EF score from baseline to 3 and 6 months post-therapy.
- Percentage of subjects that achieve minimal clinically important difference (MCID) in IIEF-EF from baseline to 3 and 6 months post-therapy.
- Percentage of subjects who either decrease or discontinue use of PDE5i after three months post-therapy

4. Study Location

The study will be funded by the CTSI pilot award (GR019191) and coordinated by the University of Miami (UM), Miller School of Medicine, Desai Sethi Urology Institute. All

study visits will take place in the Department of Urology clinics, (PAC: [name], University of Miami Miller School of medicine, Miami, FL. & Lennar: [name]) PRP preparation and SWT therapy administration will take place in the PAC andrology lab and clinic.

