4.1 Additional Study Sites

No additional study sites.

5. Study Population

15 males with ED of organic origin and diabetes. All patients will be regular PDE5i users/responders. Men with ED will be evaluated by IIEF-EF domain and eligible patients will be enrolled in this open label pilot study. Participants who do not meet eligibility criteria will be considered a screen failure and will not receive the study therapy.

5.1 Inclusion criteria:

In order to participate in this study, a patient must:

- 1) Be Male.
- 2) Be 30 to 80 years of age (inclusive).
- 3) Be able to provide written informed consent.
- 4) Have a diagnosis of mild to moderate ED (12-21) or mild ED (22-25) based on IIEF-EF questionnaire score.
- 5) Have diagnosis of Diabetes Mellitus (Type 1 or Type 2) as documented by history of hemoglobin A1C > 7% OR on medical therapy for Diabetes.
- 6) Be in a stable relationship and have a minimum of 2 sexual attempts per month for at least one month prior to enrollment.
- 7) Agree to comply with all study related tests/procedures.

5.2 Exclusion criteria:

In order to participate in this study, a patient must not have any of the following:

- 1) Previous penile surgery of any kind (except circumcision and condyloma removal), such as penile lengthening, penile cancer surgery, penile plication, grafting.
- 2) Previous history of priapism, penile fracture, Peyronie's Disease, or penile curvature that negatively influences sexual activity.
- 3) Abnormal morning serum testosterone level defined as a value lower than 300 ng/dL (±5%).
- 4) Psychogenic ED as determined by study investigator.
- 5) Patients using ICI for management of ED
- 6) Patients with generalized polyneuropathy, neurological conditions, or psychiatric disease (such as bipolar disorder or depression).
- 7) Have a serious comorbid illness or condition that, in the opinion of the investigator, may compromise the safety or compliance of the subject or preclude successful completion of the study.
- 8) History of consistent treatment failure with PDE5 inhibitors for therapy of ED.
- 9) Poorly controlled diabetes as indicated by Hemoglobin a1c > 7.5%.
- 10) Use of antiplatelet medication.

6. Identification and Enrollment of Subjects

6.1 Recruitment and Pre-screening

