6.4 Withdrawal Criteria

All subjects who either screen fails, is withdrawn from the study, or has completed all visits should be de-enrolled from the research database within 2 business days, in accordance with university policies (or respective institutional policy).

Subjects may be withdrawn from the study for any of the following reasons:

- a) A subject does not meet the eligibility criteria (the subject will be considered a screen failure).
- b) A subject withdraws consent.
- c) A subject expires during protocol participation from causes other than the study treatment (not due to adverse events).
- d) At the discretion of the principal investigator for issues of non-compliance, or other behavioral factors.

7. Procedures Involved

15 men with Erectile Dysfunction (ED) of organic origin, that meet all of the inclusion and none of the exclusion criteria, will be enrolled to receive PRP+SWT in an open-label fashion.

Autologous PRP injection + SWT therapy. All subjects in this group will receive 2 sessions of autologous PRP penile injection with 28 ± 2 day treatment interval. 5mL of PRP will be injected at each session. Additionally, patients will receive a total of 3600 shocks over a five-week period, starting at initial PRP injection.

7.1 Schedule of Events:

-

The events table for the conduct of this study is shown below:

Table1:

Schedule of Events		Screening			Follow Up				
Time Point		0-30 days	Week 0	Week 1	Week 2	Week 3	Week 4	Month 3	Month 6
Eve	nt	before randomization	Day 0	Day 7 ± 2	Day 14 ± 2	Day 21 ± 2	Day 28 ± 2	Day 90 ± 14	Day 180 ± 14
Infor	med Consent	x							
Dem	ographics	x							
Medi	cal History	x							
Phys	ical Exam	x							
Dopp	oler Ultrasound	x							X
aires	IIEF	x						X	x
tionna	EDITS							X	x
Ques	VAS		x	x	x	x	x		
Labo	ratory Tests*	x							
EPC	-CFUs	X						X	Х
Brac	hial FMD	X						Х	Х
PRP Injection			х				х		
Shockwave Therapy			Х	Х	Х	Х	Х		
Concomitant Medications/Therapy		x	x	х	х	x	x	x	x
Review Adverse Events			х	x	x	x	х	x	x

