- 7.2.10 Endothelial Progenitor Cell Colony Forming Units (EPC-CFUs): Peripheral blood samples will be collected from participants for isolation of EPCs using Ficoll-Paque density gradient. Plasma will be aliquoted and stored for future analysis. Five million cells will be seeded on 6-well Fibronectin-coated dishes (BD Biosciences) in CFU-Hill medium (Stem Cell Technologies, cat#05900)4 and incubated at 37°C in humidified 5% CO2. Non-adherent cells will be collected after 48 hours, and 1 million cells will be seeded on 24-well Fibronectin-coated dishes. On day 5, EPC-CFUs will be counted in 6 wells and the average will be obtained.
- **7.2.11** Brachial Artery Flow Mediated Dilation (FMD): FMD% is a non-clinical measure; it is a tool used specifically for research to obtain an understanding the functionality of the vascular endothelium. 2D ultrasound will be used to measure Flow Mediated

Diameter percent change (FMD%). All measurements of the brachial artery diameter and FMD% will be performed in the morning, in a quiet and dark room and at controlled ambient temperature. Subjects will fast overnight and refrain from consuming caffeine, nicotine, or other stimulants for at least 8 hours prior to ultrasound and should refrain from vigorous exercise for at least 4 hours prior to ultrasound. Subjects are permitted to drink water and take medications (except PDE5 inhibitors) as usual. The subject will rest for 10 minutes in the supine position prior to scan. The subject's right arm will be comfortably immobilized in an extending position, allowing for ultrasound scanning of the brachial artery 5–10 cm above the antecubital fossa. In each examination, recording of vessel images will be followed by inflation of a cuff to supra-systolic pressure (40 to 50 mmHg above systolic pressure) for 5 minutes. Then the cuff will be deflated, and the brachial artery diameter will be imaged and recorded for 3 minutes.

- **7.2.12** *Platelet-Rich Plasma (PRP) Injection*: Approximately 120mL of blood will be collected from participants for preparation of investigational product. Refer to Section 8 for description of Investigational Product (IP) preparation and administration.

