10.2 Specimen Banking

Bio-specimens will be reserved for future testing and stored at -80 degrees Celsius in equipment maintained by ISCI in the Biomedical Research Building (BRB) (address: [name]). Each specimen must have a corresponding requisition form to track the chain of custody from time of collection to time of processing and/or storage.

11. Safety Monitoring and Reporting

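### Nothing in the protocol keeps the person counting EPC colonies from knowing whether a sample was taken before or after treatment, and no control arm can cancel a reader shift

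*Combined protocol and SAP*

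**What the plan says.** The Protocol Synopsis gives the design as "Single arm, Open Label, Pilot Trial", and Section 7 says that the men "will be enrolled to receive PRP+SWT in an open-label fashion". Section 5 sets the sample at "15 males with ED of organic origin and diabetes".

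Section 3.1 lists seven primary markers: eNOS, nNOS, VEGF, CD-31, and the group described as "systemic markers of endothelial function (EPCs, SDF-1α, and SCF". Of these, only EPCs have a described assay, the colony-forming-unit count in Section 7.2.10. The schedule in Section 7.1 places that assay at screening, Month 3 and Month 6. The reading rule is one sentence: "On day 5, EPC-CFUs will be counted in 6 wells and the average will be obtained". It names no reader, colony definition, automated count, second reading or masking.

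Brachial FMD (Section 7.2.11) follows the same three-visit schedule. Its acquisition is tightly controlled: measurements "will be performed in the morning, in a quiet and dark room and at controlled ambient temperature". For the images themselves the text says: "Then the cuff will be deflated, and the brachial artery diameter will be imaged and recorded for 3 minutes". It does not say who measures the diameters or what that person may know. FMD does not appear among the primary, secondary or exploratory endpoints in Section 3.

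Two passages touch on specimen labelling. Section 10.2 says: "Each specimen must have a corresponding requisition form to track the chain of custody from time of collection". Section 14.3 requires stored biospecimens to be coded so that they carry no identifiers. Neither says whether the visit is hidden from the laboratory.

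**The concern.** With one arm, the effect on a marker is estimated as follow-up minus screening. Anything that moves all follow-up readings in one direction enters that estimate in full. In a randomised trial, a reader who drifts upward at later visits does so in both arms and the drift largely cancels. Here there is no second arm.

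A manual colony count involves judgement about what counts as a colony. A counter who knows the visit also knows treatment status and may, without intending to, count more generously after treatment. Averaging six wells reduces random counting error but leaves untouched a shift that all six share.

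The gap has to be closed before the first culture. Once colonies have been counted live by someone who knows the visit, masking cannot be added later.

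**Working it through.** **Is masked reading specified anywhere?** Four places could supply it.

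- Section 7.2.10 (EPC-CFU): culture steps and a well average; nothing on the reader.
- Section 7.2.11 (FMD): acquisition conditions only; nothing on the reader.
- Section 10.2: a form follows the specimen from collection. Its contents are not given, so it neither shows nor hides the visit on the face of the text.
- Section 14.3: coding removes the man's identity and concerns stored material. Masking to visit is not stated.

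No masked or independent assessor is mentioned elsewhere. The finding is therefore an omission: nothing prevents unmasked reading.

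**How large could the effect be?** The plan gives no power calculation, SD, effect size or reader variability, so it has no figure to reproduce. What follows is an illustration.

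Inputs from the documents: n = 15 (Section 5) and α = 0.05 (Section 12.1).

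Assumptions:
- A two-sided test, since sidedness is not stated.
- A paired t-test of one follow-up visit against screening. Section 12.1 describes treatment-versus-control comparisons, which a single-arm trial cannot make.
- A true mean change of zero.
- A constant reader shift b, in SD units of the within-subject change.
- n = 12 as a dropout sensitivity.

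The test statistic follows a noncentral t distribution with n − 1 degrees of freedom and noncentrality b × √n. The false-positive rate is the probability that |t| exceeds its critical value.

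For n = 15, √15 = 3.873 and the critical value on 14 df is 2.145. A mean change of 2.145 / 3.873 = 0.55 SD is therefore just significant.

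| Assumed shift b (SD) | Noncentrality, n = 15 | False-positive rate, n = 15 | False-positive rate, n = 12 |
|---|---|---|---|
| 0 | 0 | 5.0% | 5.0% |
| 0.1 | 0.39 | 6.5% | 6.2% |
| 0.25 | 0.97 | 14.7% | 12.4% |
| 0.5 | 1.94 | 43.8% | 35.3% |

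A simulation of 200,000 trials at n = 15 gave 4.9% at b = 0 and 43.9% at b = 0.5, in agreement with the formula. A shift of about 0.54 SD would give an even chance of a false change. A shift of 0.1 SD would do little harm.

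**The case against.** The strongest reply is that silence is not evidence. A reader might infer that the counter will know the visit, because a requisition form follows the tube from collection. The documents do not support that. They do not say what the form shows or what the counter sees, Section 10.2 sits under banking for future testing, and the example subject code in Section 14 carries no visit. Laboratory labelling often lives in an SOP. This stands, and it limits the point to the absence of a safeguard.

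Other stronger readings also fail:

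- **That FMD reader bias affects the primary endpoint.** FMD is scheduled but is not listed as an endpoint.
- **That the whole primary endpoint is exposed.** EPCs are one marker of seven, and equating them with EPC-CFU is a reasonable inference, since no other EPC assay is described. How the other six are measured is not stated.
- **That masking is the only safeguard available.** A written colony definition, automated counting or duplicate reading would also limit a reader shift.
- **That penile Doppler should be re-read masked as well.** Section 7.2.5 lets results from the previous 12 months be taken from the medical record, so baseline images may not be available.

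It is also fair to say that the shift sizes are chosen, not observed, and that masking fresh cultures works fully only if samples from before and after treatment pass through the laboratory in the same period. The protocol gives no accrual calendar, so that overlap cannot be assumed.

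None of this removes the core point. Open-label treatment does not require open-label reading, and the design has no comparison group to absorb a reader shift.

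**Conclusion.** The point holds in a limited form. For the only primary marker with a described assay, the protocol leaves reader expectation uncontrolled in a design where it cannot cancel. The false-positive rate would stay near nominal for a very small shift (about 6.5% at 0.1 SD) and reach about 15% at 0.25 SD and 44% at 0.5 SD with 15 men; with 12 men the figures are about 6%, 12% and 35%. These rest on an assumed paired t-test, a two-sided level, no true change and assumed shifts. The documents do not allow the actual shift to be estimated.

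This is a low-cost improvement that should be made before the first sample is cultured. It does not show that the results will be biased. If masking reduces the shift to zero, the rate for that comparison returns to 5%. Regression to the mean, the stopping of PDE5 inhibitors under Section 7.2.14 and assay drift would still be confounded with treatment.

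**What to change.** **Section 7.2.10.** Label EPC tubes and culture plates with a random specimen code that shows no subject number or visit. Keep the key linking code, requisition form and visit in REDCap, which the study already uses (Section 14.2), with no access for the counter. This preserves the chain of custody required by Section 10.2. Enter the six-well counts against the code before anyone unmasks the visit. A written colony definition would complement this.

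**Section 7.2.11.** Have the recorded FMD images measured offline, with labels removed and in random order. State that this protects a supportive measure, or clarify FMD's endpoint status in Section 3.

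**Cost.** A random code list, slightly more labelling work, a short addition to the laboratory procedure, and later FMD results. Whoever counts or measures can do so under code, so masking itself adds no reader, visit or burden on the men. For fresh cultures the masking is only partial if pre- and post-treatment samples from different men do not overlap in time, and the report should say so.

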- **7.2.13** *Shockwave Therapy (SWT)*: In the treatment group, patients randomized will receive 5 weekly sessions, in which 720 shocks of treatment energy will be applied in every session to each treated region (left and right corpora cavernosa and crura) for a total of 3,600 shocks. Refer to Section 8 for description of Investigational Product (IP) preparation and administration.
- **7.2.14** *Concomitant Medications:* Review of current use of prescription and over the counter (OTC) medications. Participants must discontinue use of PDE5i medications throughout the duration of the study.
- **7.2.15 Review Adverse Events:** Refer to Section 11 for description and reporting of adverse and serious adverse events

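### Section 7.2.11 has an all-diabetic cohort fast overnight for research-only FMD scans with usual medication allowed, and gives no instruction for drugs that can cause hypoglycaemia

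*Combined protocol and SAP*

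**What the plan says.** Section 7.2.11 describes the scan as follows: "FMD% is a non-clinical measure; it is a tool used specifically for research". It is done in the morning. On preparation: "Subjects will fast overnight and refrain from consuming caffeine, nicotine, or other stimulants for at least 8 hours prior to ultrasound". On medicines: "Subjects are permitted to drink water and take medications (except PDE5 inhibitors) as usual". Table 1 places FMD at screening, Month 3 and Month 6.

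Inclusion criterion 5 in Section 5.1 requires "Diabetes Mellitus (Type 1 or Type 2) as documented by history of hemoglobin A1C > 7% OR on medical therapy for Diabetes". Exclusion criterion 9 in Section 5.2 removes "Poorly controlled diabetes as indicated by Hemoglobin a1c > 7.5" per cent. None of the ten exclusions names insulin or any other glucose-lowering drug.

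Two general provisions bear on the point. Section 7.2.14 calls for "Review of current use of prescription and over the counter (OTC) medications", which Table 1 schedules at all three FMD visits. Exclusion 7 lets the investigator exclude a man whose serious comorbid condition "may compromise the safety or compliance of the subject or preclude successful completion of the study".

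On recording, Section 7.2.15 says: "Refer to Section 11 for description and reporting of adverse and serious adverse events". Section 11.1 keeps urological and reproductive events of any grade but other events only above grade 2, and 11.1.2 has all grade 3 to 5 events entered in the database. Section 13.1, in contrast, undertakes to record all adverse events systematically at each visit.

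**The concern.** The protocol is not merely silent about medicines on the fasting morning. It addresses them, permits them in general, and makes one exception, for a class that 7.2.14 already requires subjects to stop for the whole study. In a cohort where every man is diabetic, the drugs for which fasting matters most fall under the general permission. A man could take his usual insulin, eat nothing, and be fully compliant.

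What is at stake is subject safety. The fast serves a research measurement that is not among the endpoints in Section 3, so the subject gets no clinical return for the risk. A second question is whether an episode would be seen in the trial data at all.

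**Working it through.** The plan gives no figure to reproduce. The check is a reading of every section that could hold an instruction, followed by a count of exposure.

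**1. Is there an instruction for glucose-lowering drugs on FMD mornings?**

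| Place | What it provides | Fasting instruction for these drugs? |
|---|---|---|
| 5.1, criterion 5 | Admits men on drug treatment for diabetes | No |
| 5.2, ten exclusions | Criterion 9 removes poor control; treated, controlled men remain | No |
| 7.1, Table 1 | Timing only | No |
| 7.2.11 | Overnight fast; usual medication; PDE5 inhibitors the only exception | No |
| 7.2.14 | Medication review; PDE5 inhibitors stopped | No |
| 7.3 | Visit descriptions | No |
| 11 and 13.1 | Event definitions and risks; hypoglycaemia is not listed as a risk | No |

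**2. How many fasts could be affected?** Inputs: 15 subjects (Section 5) and 3 FMD visits per subject (Table 1). Let k be the number of enrolled men taking insulin or another drug that can cause hypoglycaemia. The documents do not give k, so it runs from 0 to 15. Maximum number of fasts = 3 × k.

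| k (assumed) | Fasts |
|---|---|
| 0 | 3 × 0 = 0 |
| 1 | 3 × 1 = 3 |
| 5 | 3 × 5 = 15 |
| 10 | 3 × 10 = 30 |
| 15 | 3 × 15 = 45 |

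These are exposures among enrolled men. The documents hold nothing from which to compute a hypoglycaemia rate.

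**3. Would an episode be recorded?**

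- *Grade 1 or 2.* Section 11.1 leaves it out, as a non-urological event not above grade 2. Section 13.1 would include it. The pointer from 7.2.15 to Section 11 favours the narrower rule, but the text does not settle the conflict.
- *Grade 3 to 5.* Section 11.1.2 has it entered.
- *At screening.* Table 1 marks adverse event review from Week 0 onward and not at screening, where the first scan takes place. Section 7.3.1 lets screening share a day with the first treatment, and the Week 0 review then falls on that day. When the visits are separate, no scheduled review collects an event of any grade at the screening scan itself.
- *Serious.* The definition in 11.2 includes life-threatening events and hospital stays over 24 hours, whatever the cause. A severe episode around the Month 3 or Month 6 scan could therefore count toward the Serious Adverse Event endpoint in 3.2.

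**The case against.** The best reply is that the wording permits usual medication and does not direct dosing without food. A drug normally taken with breakfast is still taken in the usual way if it is taken with a later breakfast. The timed steps of the scan are short: 10 minutes of rest, 5 of cuff inflation and 3 of recording, or 18 minutes in all. For such drugs the fast is mainly a delayed meal. This narrows the gap, but it does not reach long-acting drugs or drugs taken at a fixed time.

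A second reply is that clinicians will manage this. Medication review takes place at all three FMD visits, and exclusion 7 allows discretion. Both stand as partial safeguards, though neither mentions fasting. A review at the scan visit also comes after the fast has begun.

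A third is that the consent form may carry the advice, since 6.3.1 says that it covers procedures and risks. That cannot be ruled out. The point is therefore limited to the protocol text, which would still give the general permission.

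A fourth is that k may be zero: criterion 5 also admits men on a history of raised HbA1c, and the type of medical therapy is not specified. This is correct, and it is why the range starts at 0.

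A reader might also infer that the protocol tells men to take insulin while fasting, or that mild episodes will certainly go unrecorded. The first mistakes permission for direction. The second overlooks Section 13.1.

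**Conclusion.** The point holds as a gap in a safety instruction. Section 7.2.11 imposes an overnight fast for a research-only scan up to three times per man, gives general permission for usual medication in a wholly diabetic cohort, and no protocol section available for review qualifies that permission for drugs that can cause hypoglycaemia. Exposure is 0 to 45 fasts, depending on a number of treated men that the documents do not state. The link from such a drug taken without food to hypoglycaemia is ordinary clinical reasoning and is not taken from the documents.

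Recording of mild episodes is ambiguous, and the screening scan has no marked adverse event review of its own. A reader might infer that the efficacy results are at risk. The documents do not support that: FMD is not a listed endpoint. The Serious Adverse Event endpoint is different, because a severe episode during follow-up could enter it.

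This is a cheap improvement. Confidence is high about the protocol wording, and no claim is made about how often harm would occur.

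**What to change.** In 7.2.11, replace the medication sentence with wording such as: *Water and regular medications are allowed, except PDE5 inhibitors. Subjects on insulin or another drug that can cause hypoglycaemia will receive individual clinician advice on dose and timing before each fasting FMD visit.* This sets no dosing rule. A blanket order to hold or adjust all glucose-lowering drugs would be too broad: some need no change, and it would also apply to insulin in men with Type 1 diabetes.

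In 11.1, state that hypoglycaemia around any FMD visit, including screening, is recorded at any grade. Mark adverse event review at screening in Table 1 so that there is an occasion to collect it, and bring 13.1 into line with 11.1.

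The cost is a brief instruction before each of up to three visits per man and a slightly higher count of recorded adverse events.
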